Previous stroke	
Binary variable (Yes / No)
 
Equals to “Yes” if the patient meets any criterion below on or in the 2 years prior to the index date:
 
17. Is hospitalized at least once with any discharge diagnosis (i.e., main, related or associated diagnosis) of stroke (ischemic or haemorrhagic)
 
ICD-10 codes: I60.x, I61.x, I62.9, I63.x, I64.x, G45.x, G46.x, G81.x, S06.4, S06.5, S06.6
 
OR
 
 – Is covered by the LTD status for stroke (ischemic or haemorrhagic) at least one day 
ICD-10 codes: I60.x, I61.x, I62.9, I63.x, I64.x, G45.x, G46.x, G81.x, S06.4, S06.5, S06.6
 
Equals to “No” in other cases

Moreover, all the variables used to define stratification groups will be derived for each patient selected in the study population ([Table VII](#)).

Table VI. Derived variables for the selection of the population – Stratifications

Variable	Definition
Age groups	Categorical variable (<80, 80-90, >90 years old) See Table III
Heart failure history (for Modified CHAD ₂ DS ₂ VASC score strata derivation)	Binary variable (Yes / No) Derived based on (24)

Equals to "Yes" if the patient meets any criterion below on or in the 2 years prior to the index date:

- Is hospitalized at least once with any diagnosis (i.e., main, related or associated diagnosis) of cardiac failure

ICD-10 codes: I50.x, I11.0, I13.0, I13.2, I13.9

OR

- Is covered by the LTD status for cardiac failure at least one day

ICD-10 codes: I50.x, I11.0, I13.0, I13.2, I13.9

Equals to "No" in other cases

Hypertension history (for Modified CHAD ₂ DS ₂ VASC score strata derivation)	Binary variable (Yes / No) Derived based on (24) Equals to "Yes" if the patient meets any criterion below on or in the 2 years prior to the specified date:

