Congestive heart failure (for ACCI derivation)	
Binary variable (Yes / No)
 
Derived based on (20,23)
 
Equals to "Yes" if the patient meets any criterion below on or in the 2 years prior to the index date:
 
 - Is hospitalized at least once with any diagnosis (i.e., main, related or associated diagnosis) of congestive heart failure 
ICD-10 codes: I110;I130;I132;I50
 
OR
 
 - Is covered by the LTD status for congestive heart failure at least one day 
ICD-10 codes: I110;I130;I132;I50
 
Equals to "No" in other cases

Peripheral vascular disease (for ACCI derivation)	
Binary variable (Yes / No)
 
Derived based on (20,23)
 
Equals to "Yes" if the patient meets any criterion below on or in the 2 years prior to the index date:
 
 - Is hospitalized at least once with any diagnosis (i.e., main, related or associated diagnosis) of peripheral vascular disease 
ICD-10 codes: I70.x, I71.x, I73.1, I73.8, I73.9, I77.1, I79.0, I79.2, K55.1, K55.8, K55.9, Z95.8, Z95.9
 
OR
 
 - Is covered by the LTD status for peripheral vascular disease at least one day 
ICD-10 codes: I70.x, I71.x, I73.1, I73.8, I73.9, I77.1, I79.0, I79.2, K55.1, K55.8, K55.9
 
Equals to "No" in other cases

Cerebrovascular disease (for ACCI derivation)	
Binary variable (Yes / No)
 
Derived based on (20,23)
 
Equals to "Yes" if the patient meets any criterion below on or in the 2 years prior to the index date:

- Is hospitalized at least once with any diagnosis (i.e., main, related or associated diagnosis) of cerebrovascular disease

ICD-10 codes: G45.x, G46.x, H34.0, I60.x, I61.x, I62.x, I63.x, I64.x, I65.x, I66.x, I67.x, I68.x, I69.x

OR

- Is covered by the LTD status for cerebrovascular disease at least one day

ICD-10 codes: G45.x, G46.x, H34.0, I60.x, I61.x, I62.x, I63.x, I64.x, I65.x, I66.x, I67.x, I68.x, I69.x

Equals to "No" in other cases

Moderate-to-severe

**renal disease (for
ACCI derivation)**

Binary variable (Yes / No)

Derived based on (20,23)

Equals to "Yes" if the patient meets any criterion below on or in the 2 years prior to the index date:

- Is hospitalized at least once with any diagnosis (i.e., main, related or associated diagnosis) of moderate-to-severe renal disease

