ICD-10 codes: I12.0, I13.1, N03.2, N03.3, N03.4, N03.5, N03.6, N03.7, N05.2, N05.3, N05.4, N05.5, N05.6, N05.7, N18.x, N19.x, N25.0, Z49.0, Z49.1, Z49.2, Z94.0, Z99.2

OR

- Is covered by the LTD status for moderate-to-severe renal disease at least one day

ICD-10 codes: I12.0, I13.1, N03.2, N03.3, N03.4, N03.5, N03.6, N03.7, N05.2, N05.3, N05.4, N05.5, N05.6, N05.7, N18.x, N19.x, N25.0

OR

- Has at one reimbursement for a dialysis session performed at hospital or in outpatient settings

ICD-10 codes: Z94.1, Z94.2

CCAM codes: JVJB001, JVJF004, JVJF008, JVRP004, JVRP007, JVRP008, YYYY007

PRS codes: 2121, 2122, 2123, 2124, 2125, 2126, 2127, 2128, 2129, 2131, 2132, 2133, 2134, 2135, 2136, 2137, 2138, 2139, 2140, 2142, 2143, 2144, 2145, 2146, 2147, 2334

GHM codes: 28Z01Z, 28Z02Z, 28Z03Z, 28Z04Z, 11K021, 11K022, 11K023, 11K024, 11K02J

Equals to "No" in other cases	
Mild liver disease (for ACCI derivation)	
Binary variable (Yes / No)
 
Derived based on (20,23)
 
Equals to "Yes" if the patient meets any criterion below on or in the 2 years prior to the index date:
 
 - Is hospitalized at least once with any diagnosis (i.e., main, related or associated diagnosis) of mild liver failure 
ICD-10 codes: B18.x, K70.0, K70.1, K70.2, K70.3, K70.9, K71.3, K71.4, K71.5, K71.7, K73.x, K74.x, K76.0, K76.2, K76.3, K76.4, K76.8, K76.9, Z94.4
 
OR
 
 - Is covered by the LTD status for mild liver disease at least one day 
ICD-10 codes: B18.x, K70.0, K70.1, K70.2, K70.3, K70.9, K71.3, K71.4, K71.5, K71.7, K73.x, K74.x, K76.0, K76.2, K76.3, K76.4, K76.8, K76.9

Equals to "No" in other cases	
Moderate-to-severe liver disease (for ACCI derivation)	
Binary variable (Yes / No)
 
Derived based on (20,23)
 
Equals to "Yes" if the patient meets any criterion below on or in the 2 years prior to the index date:
 
 - Is hospitalized at least once with any diagnosis (i.e., main, related or associated diagnosis) of moderate-to-severe liver failure 
ICD-10 codes: I85.0, I85.9, I86.4, I98.2, K70.4, K71.1, K72.1, K72.9, K76.5, K76.6, K76.7
 
OR
 
 - Is covered by the LTD status for moderate-to-severe liver disease at least one day 
ICD-10 codes: I85.0, I85.9, I86.4, I98.2, K70.4, K71.1, K72.1, K72.9, K76.5, K76.6, K76.7

Equals to "No" in other cases	

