Chronic pulmonary disease (for ACCI derivation)	
Binary variable (Yes / No)
 
Derived based on (20,23)
 
Equals to "Yes" if the patient meets any criterion below on or in the 2 years prior to the index date:

- Is hospitalized at least once with any diagnosis (i.e., main, related or associated diagnosis) of chronic pulmonary disease

ICD-10 codes: I27.8, I27.9, J40.x, J41.x, J42.x, J43.x, J44.x, J45.x, J46.x, J47.x, J60.x, J61.x, J62.x, J63.x, J64.x, J65.x, J66.x, J67.x, J68.4, J70.1, J70.3

OR

- Is covered by the LTD status for chronic pulmonary disease at least one day

ICD-10 codes: I27.8, I27.9, J40.x, J41.x, J42.x, J43.x, J44.x, J45.x, J46.x, J47.x, J60.x, J61.x, J62.x, J63.x, J64.x, J65.x, J66.x, J67.x, J68.4, J70.1, J70.3

OR

- Has reimbursements for at least 3 dispensations at pharmacy of any antbronchodilator drugs

ATC codes: R03AB03, R03AC02, R03AC03, R03AC04, R03AC08, R03AC12, R03AC13, R03AC18, R03AK03, R03AK04, R03AK06, R03AK07, R03BA01, R03BA02, R03BA03, R03BA05, R03BB01, R03BB02, R03BB04, R03BC01, R03BC03, R03CC02, R03CC03, R03CC12, R03DA04, R03DA05, R03DA08, R03DC03, R03DX03, R03DX05

Equals to "No" in other cases

Dementia (for ACCI derivation)	Binary variable (Yes / No) Derived based on (20,23) Equals to "Yes" if the patient meets any criterion below on or in the 2 years prior to the index date: - Is hospitalized with a main or related diagnosis of dementia ICD-10 codes: F00.x, F01.x, F02.x, F03.x, F05.1, G30.x, G31.1 OR - Is covered by the LTD status for dementia at least one day ICD-10 codes: F00.x, F01.x, F02.x, F03.x, F05.1, G30.x, G31.1 OR - Has reimbursements for at least 3 dispensations at pharmacy of any anti-Alzheimer drugs ATC codes: N06DA01, N06DA02, N06DA03, N06DA04, N06DX01
	Equals to "No" in other cases

Connective tissue disease	Binary variable (Yes / No) Derived based on (20,23)
	Equals to “Yes” if the patient meets any criterion below on or in the 2 years prior to the index date:
	
 - Is hospitalized at least once with any diagnosis (i.e., main, related or associated diagnosis) of connective tissue disease
	ICD-10 codes: M05.x, M06.x, M31.5, M32.x, M33.x, M34.x, M35.1, M35.3, M36.0
	OR
	
 - Is covered by the LTD status for connective tissue disease at least one day
	ICD-10 codes: M05.x, M06.x, M31.5, M32.x, M33.x, M34.x, M35.1, M35.3, M36.0
	Equals to “No” in other cases.

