Hepatic cirrhosis/fibrosis, liver failure (for contraindications to OAC)	
Binary variable (Yes / No)
 
Equals to “Yes” if the patient meets any criterion below on or in the 2 years prior to the index date:
 
 – Is hospitalized at least once with any diagnosis (i.e., main, related or associated diagnosis) of hepatic impairment 
ICD-10 codes: K70.4, K71.1, K72.1, K72.9, K76.5, K76.6, K76.7
 
OR
 
 – Is covered by the LTD status for hepatic impairment at least one day 
ICD-10 codes: K70.4, K71.1, K72.1, K72.9, K76.5, K76.6, K76.7
 
Equals to “No” in other cases

Table XIII. Derived variables for the medical history and comorbidities

Variable	Definition
Cerebrovascular diseases (CBVD)	
Binary variable (Yes / No)
 
See Table VI

Coronary arterial diseases (CAD)	
Binary variable (Yes / No)
 
See Table V

Dementia	
Binary variable (Yes / No)
 
See Table VI

Congestive Heart failure	
Binary variable (Yes / No)
 
Equals to “Yes” if the patient is hospitalized with any discharge diagnosis (i.e., main, related or associated diagnosis) of congestive heart failure, on or in the 2 years prior to the index date
 
OR
 
Is covered by the LTD status for congestive heart failure at least one day
 
ICD-10 codes: I50.2, I50.3, I50.4
 
Equals to “No” in other cases

Peripheral arterial disease	
Binary variable (Yes / No)
 
Equals to “Yes” if the patient is hospitalized with any discharge diagnosis (i.e., main, related or associated diagnosis) of peripheral arterial disease, on or in the 2 years prior to the index date
 
OR
 
Is covered by the LTD status for peripheral arterial disease at least one day
 
ICD-10 codes: I70.0-I74, I771
 
Equals to “No” in other cases

Other vascular diseases	
Binary variable (Yes / No)
 
Equals to “Yes” if the patient is hospitalized with any discharge diagnosis (i.e., main, related or associated diagnosis) of peripheral arterial disease or is covered by the LTD status for peripheral arterial disease at least one day, in the 2 years prior to the index date
 
OR
 
Is covered by the LTD status for other vascular diseases at least one day
 
ICD-10 codes: I79.0, I79.2, K55.1, K55.8, K55.9, Z95.8, Z95.9.
 
Equals to “No” in other cases,

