Sleep disorders	
Binary variable (Yes / No)
 
Equals to “Yes” if the patient is hospitalized with any discharge diagnosis (i.e., main, related or associated diagnosis) of sleep disorders, on or in the 2 years prior to the index date
 
ICD-10 codes: G47.x
 
Equals to “No” in other cases

Active cancer	
Binary variable (Yes / No)
 
See Table V

Age adjusted Charlson Comorbidity Index (ACCI) adapted to SNDS data	
Continuous variable (point)
 
See Table V

Malnutrition	
Binary variable (Yes / No)
 
See Table V

Morbid Obesity	
Binary variable (Yes / No)
 
See Table V

Anemia	
Binary variable (Yes / No)

	
Equals to "Yes" if the patient is hospitalized with any discharge diagnosis (i.e., main, related or associated diagnosis) of anemia, on or in the 2 years prior to the index date
 
OR
 
Is covered by the LTD status for anemia at least one day
 
ICD-10 codes : D50.x, D53.x
 
Equals to "No" in other cases

Chronic obstructive pulmonary disease (COPD)	
Binary variable (Yes / No)
 
Equals to "Yes" if the patient is hospitalized with any discharge diagnosis (i.e., main, related or associated diagnosis) of chronic obstructive pulmonary disease, on or in the 2 years prior to the index date
 
OR
 
Is covered by the LTD status for COPD at least one day
 
ICD-10 codes: J44.9
 
Equals to "No" in other cases

History of Diabetes	
Binary variable (Yes / No)
 
See Table V

Risk of falls	
Binary variable (Yes / No)
 
See Table V

Poly-medicated	
Binary variable (Yes / No)
 
Equals to "Yes" if the patient has reimbursements for ≥ 5 different medications (different ATC5) in the year before the index date.
 
Equals to "No" in other cases (i.e., patient with reimbursement for < 5 different medications in the year before the index date).

At least one visit to a nursing home	
Binary variable (Yes / No)
 
See Table V

History of major bleeding	
Binary variable (Yes / No)
 
See Table VI

One or more comorbidities	
Binary variable (Yes / No)
 
See Table VI

Table XIV. Derived variables for concomitant treatments

Variable	Definition
----------	------------

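### SAP Tables XII and XIII define heart failure, COPD and the hepatic contraindication with narrower code lists than the SAP uses elsewhere or the label implies, so descriptive rows will under-count

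*SAP*

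**What the plan says.** **Heart failure.** SAP Table XIII (section 9.4.3.1) flags congestive heart failure from hospital diagnoses or long-term disease status with "ICD-10 codes: I50.2, I50.3, I50.4". Protocol Appendix 4 has the same three codes. SAP Table VI (section 9.4.1) holds two other heart-failure variables, also based on hospital diagnoses or long-term disease status. The one for the age-adjusted Charlson index (ACCI) uses "ICD-10 codes: I110;I130;I132;I50", and the one for CHA2DS2-VASc uses "ICD-10 codes: I50.x, I11.0, I13.0, I13.2, I13.9".

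**COPD.** Table XIII uses "ICD-10 codes: J44.9", again as in Protocol Appendix 4. The chronic pulmonary disease variable for the ACCI in Table VI starts with "I27.8, I27.9, J40.x, J41.x, J42.x, J43.x, J44.x, J45.x", continues to further codes, and also accepts repeated drug dispensations.

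**Hepatic contraindication.** Table XII defines a composite flag for contraindications to OAC. One component is named for hepatic cirrhosis, fibrosis or liver failure, and its codes are "K70.4, K71.1, K72.1, K72.9, K76.5, K76.6, K76.7". Mild liver disease in Table VI includes "K70.0, K70.1, K70.2, K70.3, K70.9, K71.3, K71.4, K71.5, K71.7, K73.x, K74.x". The liver item of HAS-BLED takes the whole range K70 to K77.

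**The concern.** Objective 2 is to describe patients exposed and unexposed to OAC. Heart failure bears on thromboembolic risk, and contraindications bear on why a patient is left untreated, so these rows will be read closely.

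Table A5 prints a congestive heart failure row among the comorbidities and a heart failure row in its Charlson block. The two will differ only because of the code lists, and nothing in the table will tell the reader so.

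The contraindication row in Tables A4 and A7 is the only direct report of contraindications. The protocol's table of selection criteria (section 3.2.1) lists contraindications to OAC as an exclusion, but SAP section 9.2.3.2 does not. Such patients can therefore remain in the cohort, and a component that misses part of what its label names will understate how many there are.

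**Working it through.** There is no sample-size, power or rate figure to reproduce. The check compares the code lists as sets, expanding each '.x' to the digits 0 to 9 (not every digit need be a valid code).

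| Variable | Narrow list | Comparator in the SAP | Result |
|---|---|---|---|
| Heart failure, Table XIII | I50.2, I50.3, I50.4 | CHA2DS2-VASc list: 10 I50 codes + 4 others = 14 | strict subset, 3 of 14; omits I50.0, I50.1, I50.5 to I50.9, I11.0, I13.0, I13.2, I13.9 |
| Heart failure, Table XIII | same | ACCI list: 10 + 3 = 13 | strict subset, 3 of 13; same omissions except I13.9 |
| COPD, Table XIII | J44.9 | the J44.x part of chronic pulmonary disease: 10 | strict subset, 1 of 10 |
| Hepatic contraindication, Table XII | 7 K codes | moderate-to-severe liver disease, Table VI: 11 | strict subset, 7 of 11; omits I85.0, I85.9, I86.4, I98.2 |
| Hepatic contraindication, Table XII | same | mild liver disease, Table VI | no code in common |

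**Direction.** For heart failure, the data sources and the two-year look-back match those of the Charlson variable, so only the codes differ. A strict subset of codes can flag only the same patients or fewer. The Table XIII row is therefore equal to or below the Charlson row in every column of Table A5.

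**COPD.** The comparator is a broader construct (J40 to J47 and other codes, plus drug dispensations). Only its J44 part is like for like. On that part, a patient whose only COPD code is any J44 subcode other than J44.9 is not counted.

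**Liver.** The seven codes are exactly the K codes of the list that Table VI describes as moderate-to-severe liver failure. K70.2, K70.3, K71.7 and K74.x appear only under mild liver disease and inside the HAS-BLED range. A patient coded only K74.x therefore gets a HAS-BLED liver point and counts as having mild liver disease, but has no hepatic contraindication under a label that names cirrhosis and fibrosis.

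**Where the variables go.** Heart failure and COPD are rows of Tables A5 and A8 and are listed for the clustering in Table XX. The liver variable enters only the composite contraindication row of Tables A4 and A7. The Cox covariates (Table XV and section 9.7.4.2) bring heart failure in through CHA2DS2-VASc and ACCI, and liver disease through HAS-BLED and ACCI. None of the three narrow variables defines a primary subgroup (section 9.2.3.4) or a stratum of the primary rates.

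**The case against.** **The broader information is already reported.** The Charlson block of Table A5 has rows for heart failure, chronic pulmonary disease, and mild and moderate-to-severe liver disease, and the score summaries in Table A4 use the broad lists. This is true and limits the harm: patients with K74.x are visible as mild liver disease. It does not explain two heart-failure rows that disagree, or put those patients in the contraindication row.

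**COPD has no second definition to contradict.** This stands in part. Chronic pulmonary disease is a different construct, so this is the weakest of the three items. What remains is that a variable named for COPD excludes every J44 subcode but one.

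**The hepatic variable may be meant for severe disease under a loose label.** The text of the criterion speaks of hepatic impairment, and the SAP classes K74.x as mild. That reading fits the codes, so renaming the variable is as good a remedy as adding codes. The mismatch exists either way.

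**The SAP follows the protocol.** For heart failure and COPD it does, so both documents need the edit. But the SAP already departs from Appendix 4 elsewhere: peripheral arterial disease was widened from three I70 codes to I70.0 to I74 plus I77.1.

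**Stronger readings that the documents do not support.** A reader might infer that the heart-failure row will be almost empty because of differences between versions of ICD-10. The documents give neither the subdivisions nor any code frequencies, so only equal or lower follows. A reader might also infer that the contraindication flag distorts the clustering, but Table XX does not list it. Nor can the side-by-side conflict be asserted for Table A8, whose Charlson heart failure row does not appear in the available text.

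**Conclusion.** The point holds as a descriptive error. If the SAP is programmed as written, the heart-failure and COPD rows of Tables A5 and A8 and the hepatic part of the contraindication row in Tables A4 and A7 can only be equal to or below what the SAP's broader lists, or the label, would give. Table A5 will carry two heart-failure prevalences. Heart failure and COPD also enter the exploratory clustering in their narrow form.

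The amount of under-counting cannot be derived from the documents. A reader might infer that the primary incidence rates or the adjusted hazard ratios are biased by these lists. They are not: those analyses do not use the three narrow variables, and the scores used for adjustment rest on the broader ones.

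One assumption is needed: reading K70.2, K70.3, K71.7 and K74.x as the cirrhosis and fibrosis codes relies on ICD-10 code titles, which the documents do not print. Without it, the documents still show that a variable named for cirrhosis and fibrosis carries only codes that the SAP elsewhere assigns to moderate-to-severe liver failure.

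**What to change.** - **Heart failure:** use one of the two Table VI lists in Table XIII, or drop the duplicate row. State which Table VI list feeds the Charlson heart failure row, since the two differ by I13.9.
- **COPD:** use J44.x in Table XIII.
- **Hepatic contraindication variable:** reconcile label and codes, either by adding the cirrhosis and fibrosis codes (K70.2, K70.3, K71.7, K74.x) or by renaming it to liver failure. Which conditions should count as a contraindication is for the scientific committee; the SAP needs only to make name and content agree.
- **Protocol Appendix 4:** align the heart-failure and COPD entries.

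The cost is a code-list edit in the two documents before programming. No new data source or analysis is needed, because the SAP already uses these codes for other variables.

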9.2.1.2 Index Date

Depending on the date of first evidence of AF over the study period, AF patients will be included at the following dates:

- On 1st January 2016 for **prevalent AF patients** (i.e., patients diagnosed AF during the historical period);
- On the first date of evidence of AF (first date of diagnosis of AF identified either by a LTD or the start date of a hospitalization, or the first date of OAC dispensation) for **incident AF patients**.

A patient will be considered exposed to OAC at the time of his/her inclusion if at least one dispensation of OAC is issued within 30 days after inclusion (including date of inclusion). In such a case, the index date will be the date of the first dispensation of OAC (cf. Appendix 1).

Otherwise, if no dispensation of OAC will be identified within 30 days from inclusion, the index date will be the date of inclusion.

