Beta-blockers	Binary variable (Yes / No) Equals to “Yes” if the patient has reimbursements for at least one dispensation at pharmacy of any beta-blockers, on or in the 4 months prior to the index date ATC codes: C07xxxx Equals to “No” in other cases Table V
Antihypertensives	Binary variable (Yes / No) Equals to “Yes” if the patient has reimbursements for at least one dispensation at pharmacy of any antihypertensive drug, on or in the 4 months prior to the index date ATC codes: C02xxxx, C03xxxx, C08xxxx, C09xxxx (excluding C03BA08 and C03CA01) Equals to “No” in other cases
Antiplatelet drugs	Binary variable (Yes / No) Equals to “Yes” if the patient has reimbursements for at least one dispensation at pharmacy of any antiplatelet drug, on or in the 4 months prior to the index date ATC codes: B01ACxx Equals to “No” in other cases
Other anticoagulants	Binary variable (Yes / No) Equals to “Yes” if the patient has reimbursements for at least one dispensation at pharmacy of any other anticoagulant, on or in the 4 months prior to the index date ATC codes: B01ABxx, B01AExx (except B01AE07), B01AFxx (except B01AF01 and B01AF02), B01AXxx Equals to “No” in other cases
Non-steroidal anti-inflammatory drugs (NSAIDs)	Binary variable (Yes / No) Equals to “Yes” if the patient has reimbursements for at least one dispensation at pharmacy of any NSAID, on or in the 4 months prior to the index date ATC codes: M01Axxx Equals to “No” in other cases
Oral corticoids	Binary variable (Yes / No) Equals to “Yes” if the patient has reimbursements for at least one dispensation at pharmacy of any oral corticoid, on or in the 4 months prior to the index date

	
ATC codes: H02AB
 
Equals to “No” in other cases

Proton pump inhibitors	
Binary variable (Yes / No)
 
Equals to “Yes” if the patient has reimbursements for at least one dispensation at pharmacy of any proton pump inhibitor, on or in the 4 months prior to the index date
 
ATC codes: A02BC
 
Equals to “No” in other cases

Selective serotonin reuptake inhibitor antidepressants (SSRIs)	
Binary variable (Yes / No)
 
Equals to “Yes” if the patient has reimbursements for at least one dispensation at pharmacy of any SSRI, on or in the 4 months prior to the index date
 
ATC codes: N06AB
 
Equals to “No” in other cases

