Systemic azole antifungals	
Binary variable (Yes / No)
 
Equals to “Yes” if the patient has reimbursements for at least one dispensation at pharmacy of any systemic azole antifungal, on or in the 4 months prior to the index date
 
ATC codes: J02AB, J02AC
 
Equals to “No” in other cases

Medical procedure of cardioversion	
Binary variable (Yes / No)
 
Equals to “Yes” if the patient has at least one medical procedure of cardioversion, on or in the 4 months prior to the index date
 
Codes: DERP004, DERP003
 
Equals to “No” in other cases

CYP P450 inhibitors	
Binary variable (Yes / No)
 
Equals to “Yes” if the patient has reimbursements for at least one dispensation at pharmacy of any CYP P450 inhibitors, on or in the 4 months prior to the index date
 
ATC codes: B01AC24, C05AE03, C09BB10, C01BD01, J01FAxx excepted J01FA02
 
Equals to “No” in other cases

Protease inhibitors	
Binary variable (Yes / No)

	
Equals to “Yes” if the patient has reimbursements for at least one dispensation at pharmacy of any CYP P450 inhibitors, on or in the 4 months prior to the index date
 
ATC codes: J05AE
 
Equals to “No” in other cases

Antiarrhythmics	
Binary variable (Yes / No)
 
Equals to “Yes” if the patient has reimbursements for at least one dispensation at pharmacy of any antiarythmics, on or in the 4 months prior to the index date
 
ATC codes: C01BA, C01BB, C01BC, C01BD, C01BG
 
Equals to “No” in other cases

Glucose-lowering drugs	
Binary variable (Yes / No)
 
Equals to “Yes” if the patient has reimbursements for at least one dispensation at pharmacy of any glucose-lowering drugs, on or in the 4 months prior to the index date
 
ATC codes: C10AA, C10BA, C10BX; C10AB; C10AX06; C10AX13, C10AX14
 
Equals to “No” in other cases

Lipid-lowering drugs	
Binary variable (Yes / No)
 
Equals to “Yes” if the patient has reimbursements for at least 3 dispensations at pharmacy of any glucose-lowering drug, on or in the 4 months prior to the index date:
 
ATC codes: A10Axx, A10Bxx excepted for A10BX06
 
OR
 
Has reimbursements for 2 dispensations at pharmacy of any glucose-lowering drug, of which at least one in a package containing >80 pills, on or in the 4 months prior to the index date:
 
ATC codes: A10Axx, A10Bxx excepted A10BX06
 
Equals to “No” in other cases

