9.4.3.2 Comparison of the incidence of stroke, major bleeding, death

The incidence rate ratio for each event of interest (stroke, major bleeding and death; see [Table VIII](#) for derivation of events of interest) will be compared using a Cox regression model with OAC exposure (see [Table VII](#) for derivation of exposure sequences) considered as time-dependent variable adjusted for covariates. Covariates will be derived at index date as indicated in [Table XV](#).

Table XV. Derived variables for confounders

Variable	Definition
Age	Categorical variable (<80 years old / 80–90 / >90 years old) See Table III
Sex	Binary variable (Female / Male) See Table III
Prescriber's specialty at initiation of OAC	Categorical variable (Hospital-based physician/ City cardiologist/ Generalist practitioners/Other) See Table III
Having Malnutrition	Binary variable (Yes / No) See Table III
Risk of falls	Binary variable (Yes / No) See Table III
Frail patients	Binary variable (Yes / No) See Table V
Morbid obesity	Binary variable (Yes / No) See Table VI
At least one visit to a nursing home	Binary variable (Yes / No) See Table VI
Concomitant treatments	Binary variable (Yes / No) for each concomitant treatment listed in Table XIV

For example, for antiplatelet drugs, equals to “Yes” if the patient has at least one reimbursement for an antiplatelet drug in the 4 months before the index date
	
HAS-BLED score	Categorical variable (0, 1, 2, 3, ≥ 4) See Table VI
CHAD₂DS₂VASC score	Categorical variable (0, 1, 2, 3, 4, ≥ 5) See Table VI
Age adjusted Charlson Cormordity Index (ACCI) adapted to SNDS data	Categorical variable (0, 1-2, 3-4, ≥ 5) See Table VI XII

9.4.3.3 *Estimation of the AF annual standardized incidence rate and prevalence*

All the variables in [Table XVI](#) will be derived for all AF patients in France in 2016, 2017, 2018 and 2019.

Table XVI. Derived variables for incidence and prevalence

Variable	Definition
Incident AF patient	Binary variable (Yes / No) See Table X
Prevalent AF patient	Binary variable (Yes / No) Equals to “Yes” if the patient is diagnosed AF during the historical period Patients belonging to the study population

9.4.3.4 *To describe the use of oral anticoagulants (OACs) in AF patients initiating treatment (AF patients exposed to OAC therapy)*

Table XVII. Derived variables for OAC treatment pattern

Variable	Definition

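### Concomitant-treatment covariates are read up to the first OAC dispensing in patients exposed at index but only up to inclusion in unexposed patients, so treatment begun at AF diagnosis is counted unequally

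*SAP*

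**What the plan says.** SAP 9.2.1.2 includes incident patients at first evidence of AF: the "first date of diagnosis of AF identified either by a LTD or the start date of a hospitalization", or the first OAC dispensing. If an OAC is dispensed from day 0 to day 30 after inclusion, the patient is exposed: "In such a case, the index date will be the date of the first dispensation of OAC". Otherwise, "if no dispensation of OAC will be identified within 30 days from inclusion, the index date will be the date of inclusion".

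All 17 items of Table XIV (SAP 9.4.3.1) use a 4-month window closing on the index date, that day included. For beta-blockers the criterion is "at least one dispensation at pharmacy of any beta-blockers, on or in the 4 months prior to the index date"; for cardioversion it is "at least one medical procedure of cardioversion, on or in the 4 months prior to the index date".

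SAP 9.4.3.2 carries these items into the Cox models. "Covariates will be derived at index date as indicated in" Table XV, which takes a "Binary variable (Yes / No) for each concomitant treatment listed in" Table XIV. SAP 9.7.4.2 lists them as time-fixed confounders. Table XV's own antiplatelet example, and the drug item of HAS-BLED (also a Table XV confounder), place the 4 months before the index date without including that day.

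Sensitivity analysis 1 (SAP 9.7.6) makes the inclusion date the index date for all incident patients. Protocol 3.1.2 ties the index date to first AF diagnosis wherever that is dated, so the split index date comes from the SAP.

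**The concern.** A baseline covariate should be measured at the same clinical moment whatever treatment follows. Here the end of the window depends on exposure status. Take two patients admitted with AF on the same day, both cardioverted on day 2 and both dispensed a beta-blocker on day 6. One is dispensed an OAC on day 10 and the other is not. The first is recorded as Yes on both items and the second as No on both, with no clinical difference before the OAC decision.

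The recorded covariate is then partly a marker of exposure. Adjusting for it can bias the comparison with unexposed time even when true use before AF is balanced. Tables A6 and A9 would also show treatment differences produced partly by where the window ends. Comparison of exposed with unexposed patients is secondary objective 3, and the lack of data on unexposed patients is the study's stated rationale.

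**Working it through.** **Step 1: where the window ends, counted from inclusion.**

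| Route into the study | Exposed at index | Not exposed at index |
|---|---|---|
| Hospital stay | First OAC, day 0 to +30 | Day of admission |
| LTD | First OAC, day 0 to +30 | LTD start date |
| OAC algorithm only | Day 0, which is the OAC date | Does not arise |

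The asymmetry is clearest in the first row. In the second it is partial, because AF drugs started before the LTD date are already inside the unexposed window. In the third, inclusion and index coincide, but the window still takes in the work-up before the OAC.

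**Step 2: which treatments are counted unequally.** Drugs dispensed after inclusion and before the first OAC, and a cardioversion during the index stay, count only for patients exposed at index, whichever wording applies. Drugs filled on the same day as the first OAC count under Table XIV. Under the wording of Table XV and the HAS-BLED item they do not.

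**Step 3: illustration of size.** The plan gives no figure to reproduce, so every input is an assumption:
- use before AF, p = 0.35 in both groups;
- share of the remainder who start because of AF, q = 0.10, 0.30 or 0.50 in both groups, recorded only in the exposed;
- rate ratio for use before AF, g; AF-triggered use carries no effect;
- true exposure hazard ratio 0.80, equal person-time, fixed groups, one covariate.

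Recorded prevalence is p in the unexposed and p + (1 − p)q in the exposed:
- q = 0.10: 0.35 + 0.65 × 0.10 = 0.415
- q = 0.30: 0.35 + 0.65 × 0.30 = 0.545
- q = 0.50: 0.35 + 0.65 × 0.50 = 0.675

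A Poisson model was fitted to the expected counts, with exposure and the recorded covariate as terms. Per unit of person-time, expected events are:
- exposed, recorded Yes: 0.80[pg + (1 − p)q]
- exposed, recorded No: 0.80(1 − p)(1 − q)
- unexposed, recorded Yes: pg
- unexposed, recorded No: 1 − p

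Adjusted exposed-versus-unexposed ratio (truth 0.80):

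| q | g = 0.7 | g = 1.3 | g = 1.5 | g = 2.0 |
|---|---|---|---|---|
| 0.10 | 0.816 | 0.787 | 0.780 | 0.765 |
| 0.30 | 0.845 | 0.766 | 0.747 | 0.710 |
| 0.50 | 0.872 | 0.746 | 0.718 | 0.664 |

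The crude ratio is 0.80 throughout, because true use before AF is balanced; the adjustment creates the error. With the covariate taken before AF in both groups, the adjusted ratio is 0.800.

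The plan's reference is VKA, so its ratio runs the other way. If the exposed group stands for VKA time, a true 1/0.80 = 1.25 for unexposed versus VKA becomes 1/0.787 = 1.27 to 1/0.664 = 1.51 when g is above 1, and 1/0.872 = 1.15 to 1/0.816 = 1.23 when g = 0.7.

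**The case against.** **Sensitivity analysis 1 already aligns the dates.** It covers both the event rates and the comparison, and since covariates are derived at the index date, the natural reading is that their windows move too. This has real weight. But the SAP does not say that covariates are re-derived, the shell-table notes describe the analysis only as restoring patients with an event between inclusion and index, and the main models and Tables A6 and A9 stay as they are.

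**Exposure is time-dependent.** Patients who start an OAC after day 30 carry inclusion-date covariates into exposed time, and patients who stop carry OAC-date covariates into unexposed time. This dilutes the effect without removing it, and it makes the fixed-group illustration an upper-end case. Adjustment for age, the risk scores, ACCI and frailty may absorb part of the assumed covariate effect as well.

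**The comparison tables are labelled as describing patients at index date.** They are accurate on those terms. The difficulty is that this date marks different clinical moments in the columns being compared.

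Some stronger readings are not supported:
- A reader might infer that every hazard ratio is affected. DOAC-versus-VKA contrasts among patients exposed at index share one window rule.
- A reader might infer that the primary results are affected. Those rates are standardised on age only and do not use Table XIV.
- A reader might multiply the illustration by the 17 items. Nothing in the documents suggests that SSRIs, azoles or protease inhibitors are started because of AF, and the item labelled lipid-lowering needs at least two dispensings.
- A reader might take heparin recorded in VKA starters to be overlap treatment. The documents do not address this, and it bears on a different contrast.

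**Conclusion.** The point holds in a limited form. As written, the SAP ascertains Table XIV treatments over windows that end at different clinical moments according to exposure at index, for hospital-identified patients and partly for LTD-identified ones. It then adjusts for them as time-fixed confounders. The contrasts mainly at risk are unexposed versus VKA and the exposed and unexposed columns of Tables A6 and A9. Separately, Tables XIV and XV must be reconciled on whether the index day counts.

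The asymmetry follows from the text; the size and direction of bias do not. The range of about 0.66–0.79, or 0.82–0.87 in the other direction, against a true 0.80 rests wholly on the assumed p, q and g, on one covariate and on fixed groups. It should be read as an upper-end illustration and not as a prediction for this study. The change is worth making before analysis because it is small and the affected contrast is a stated secondary objective.

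**What to change.** In Tables XIV and XV and the HAS-BLED drug item, define one window for all patients: in the 4 months before, and not including, the inclusion date. Use it in the main Cox models and in the exposed and unexposed comparison tables. This also settles the index-day conflict. Keep the index-date version only to describe co-treatment at OAC start within the exposed group. In SAP 9.7.6, state that sensitivity analysis 1 re-derives all covariates at the inclusion date.

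The cost is one date variable in the derivation programs. Three consequences should be acknowledged:
- Treatments started at AF diagnosis are no longer baseline.
- Patients included only through the OAC algorithm keep drugs from the work-up before the OAC, because their inclusion date is the OAC date. Report this as a residual limitation.
- The 2-year comorbidity windows stay anchored on the index date unless they are moved too, so the SAP should say which anchor applies to each set of covariates.
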